2.5 Correlative Studies Background

2.5.1 Pharmacokinetic Studies

While the pharmacokinetic data of single-agent INCB039110 and the combination of dabrafenib and trametinib are known, PK data of the triple combination have not been previously studied. The lack of evidence for drug-drug interactions with INCB039110 poses little risk that the clearance of dabrafenib and/or trametinib will be altered. We will collect trough samples on the first day of certain cycles in the protocol in order to measure drug concentrations of each agent if we encounter a rate of toxicity with the combination regimen that is higher than expected

The PK sampling regimen for this study is based on the following observations; steady state for trametinib was reached by approximately Day 15 and the C_{max} and AUC for dabrafenib at the RP2D are about 40% lower on Day 15 versus Day 8. In addition, accumulation of trametinib was observed in the combination study of trametinib and dabrafenib. Therefore, sampling of trough levels on day 1 of cycle 2 and cycle 4 and 6 will provide value that correspond to steady-state concentrations of dabrafenib and trametinib.

2.5.2 Biomarkers of Drug Effect

Although we do not yet know which JAK1 targets must be modulated in order for long term anti-tumor responses to be seen to the BRAF/MEK/JAK1 inhibitor combination, preliminary studies from our group

and others suggests that the RNF125-JAK1-AXL/EGFR and EGFR-SRC family kinase-STAT3 pathways may be critical for the short-term adaptive responses to BRAF inhibition and that prolonged inhibition of the Raf/MEK/ERK/CDK4/Cyclin D1 pathway is required for durable anti-tumor response. Thus, levels of JAK1 protein, downstream targets such as STAT1 and STAT3 and other proteins involved in adaptive signaling responses (EGFR, PDGR, MITF, NF- κ B) will be measured via immunohistochemistry, immunofluorescence or immunoblots from FNAs taken from accessible melanoma lesions before therapy initiation and following BRAF/MEK/JAK1 inhibitor treatment. The preferred time point for on-treatment biopsies is Cycle 1 Day 7 (\pm 3 days). Biopsies may be also taken at any time, including at the time of clinically meaningful events such as response, disease progression or adverse events of interest.

Additionally, biopsy specimens will be evaluated by Reverse Phase Protein Array (RPPA) at RPPA Core Facility, [name] Anderson Cancer Center (Texas, USA). Primary targets of interest for analysis of INCB039110 effect on relevant JAK1 target proteins in tumor biopsy tissue will be evaluated. Frozen biopsy specimens obtained during collection will be sent for analysis of relevant proteins, protein post-translational modifications (phosphorylation and other modifications) and effects on relevant signaling pathways.

2.5.3 Blood Based BRAF Assay

Our group has developed a blood-based assay that can measure circulating BRAF levels in patients with BRAF mutant melanoma. (Panka *et al.*, 2010; Panka *et al.*, 2014) Our data shows that the BRAF level is reduced in patients treated with BRAF-directed therapy (both single-agent vemurafenib and the combination of DT) and, in some patients, increases in advanced of clinical or radiographic progression by 40-60 days. (Panka *et al.*, 2014) As this assay remains under clinical development, we plan to measure serial values (pre-treatment and at the beginning of each cycle) to further interrogate the utility of this assay. All samples will be initially processed in the Translational Research Laboratory at MGH and then subsequently assayed at the BIDMC.

2.5.4 Expanded Genetic/Genomic Analysis

A number of mutations in oncogenes and tumor suppressor genes have been described in melanoma (McArthur *et al.*, 2012; TCGA). We will plan to perform expanded genomic analysis on pretreatment samples (either from pretreatment biopsies or from archived, formalin-fixed paraffin-embedded tumor blocks [FFPE]). The exact methodology for analysis has not yet been selected, though the options include NGS for mutations/deletions, nanostring for mRNA, and IHC and RPPA for protein. As it becomes clearer which methodology is best suited for the analysis as part of this protocol, a protocol amendment will be submitted that details the rationale and specific details for which technique(s) is (are) selected.

3. PARTICIPANT SELECTION

Any labs drawn on Cycle 1, Day 1 will not be used to reconfirm eligibility. Eligibility is confirmed at screening; it is not required to be reassessed on Cycle 1, Day 1.

3.1 Eligibility Criteria

3.1.1 *For Dose-Escalation Phase:* Patients must have histologically confirmed, BRAF-mutant (V600E/K) malignancy (molecularly confirmed using Cobas assay or a comparable FDA-approved assay (for exceptions, see below*) that is metastatic or unresectable, have received and tolerated prior BRAF or BRAF and MEK inhibitor (BRAF targeted) therapy or not previously received BRAF targeted therapy, and for which standard curative or palliative measures do not exist or are no longer effective.

- *If test at CLIA-certified lab used a non-FDA approved method, information about the assay must be provided to the Overall Principal Investigator (PI) for approval. (FDA approved tests for BRAF V600 mutations in melanoma include: THxID BRAF Detection Kit and Cobas 4800 BRAF V600 Mutation Test).

3.1.2 *For Dose-Expansion Phase:* Patients must have histologically confirmed, BRAF-mutant (V600E/K) melanoma (molecularly confirmed using Cobas assay or a comparable FDA-approved assay (for exceptions, see below*) that is metastatic or unresectable, have received and tolerated prior BRAF or BRAF and MEK inhibitor (BRAF targeted) therapy at full dose or not previously received BRAF targeted therapy.

- *If test at CLIA-certified lab used a non-FDA approved method, information about the assay must be provided to the Overall Principal Investigator (PI) for approval. (FDA approved tests for BRAF V600 mutations in melanoma include: THxID BRAF Detection Kit and Cobas 4800 BRAF V600 Mutation Test).

3.1.3 Patients must have measurable disease by RECIST, defined as at least one lesion that can be accurately measured in at least one dimension (longest diameter to be recorded for non-nodal lesions and short axis for nodal lesions) as ≥ 20 mm with conventional techniques or as ≥ 10 mm with spiral CT scan, MRI, or calipers by clinical exam. See Section 11 for the evaluation of measurable disease.

3.1.4 Patients may have received any number of prior lines of therapy. All prior systemic anti-cancer treatment-related toxicities must be less than or equal to Grade 1 according to the Common Terminology Criteria for Adverse Events version 4 (CTCAE version 4.0; NCI, 2009) at the time of enrollment. This does not include alopecia and Grade 1 or less peripheral neuropathy.

3.1.5 Age ≥ 18 years. Because no dosing or adverse event data are currently available on the use of INCB039110 in combination with dabrafenib and trametinib in patients < 18 years of age, children are excluded from this study, but will be eligible for future pediatric trials.

3.1.6 ECOG performance status ≤ 1 (Karnofsky $\geq 70\%$, see Appendix A).

3.1.7 Life expectancy of greater than 3 months in the opinion of the investigator.

3.1.8 Patients must have acceptable organ and marrow function as defined below:

– Leukocytes (WBCs)	$\geq 3,000/\mu\text{L}$
– absolute neutrophil count	$\geq 1,500/\mu\text{L}$
– hemoglobin	$\geq 9 \text{ g/dL}$ (patients may be transfused to this level)
– platelets	$\geq 100,000/\mu\text{L}$
– total bilirubin	$< 1.5 \times$ institutional upper limit of normal

OR

- AST(SGOT)/ALT(SGPT)	> 1.5 x institutional upper limit of normal allowed if direct bilirubin is within normal range.
- PT/INR and PTT	$\leq 2.5 \times$ institutional upper limit of normal
- Serum creatinine	$< 1.3 \times$ ULN ¹ $\leq 1.5 \text{ mg/dL}$ OR creatinine clearance $\geq 50 \text{ mL/min/1.73 m}^2$
- Potassium	$> 3 \text{ and } < 5.5 \text{ mmol/L}$
- Magnesium	$> 1.2 \text{ and } < 2.5 \text{ mg/dL}$

¹Therapeutic levels of anti-coagulation are permitted if clinically indicated, as per section 3.2.15. Thus PT/INR may be >1.3 if therapeutically anti-coagulated.

3.1.9 The effects of INCB039110, dabrafenib, and trametinib on the developing human fetus are unknown. For this reason, women of child-bearing potential must have a *negative serum pregnancy test within 14 days prior to registration and agree to use effective contraception* (barrier method of birth control, or abstinence; hormonal contraception is not allowed due to drug-drug interactions which can render hormonal contraceptives ineffective) *from 14 days prior to registration*, throughout the treatment period, and for 4 months after the last dose of study treatment. Should a woman become pregnant or suspect she is pregnant while she is participating in this study, she should inform her treating physician immediately.

Based on studies in animals, it is also known that dabrafenib may cause damage to the tissue that makes sperm. This may cause sperm to be abnormal in shape and size and could lead to infertility, which may be irreversible.

Men with a female partner of childbearing potential must have either had a prior vasectomy or agree to use effective contraception. Additionally, male subjects (including those who are vasectomized) whose partners are pregnant or might be pregnant must agree to use condoms for the duration of the study and for 4 months following completion of therapy.

3.1.10 Ability to understand and the willingness to sign a written informed consent document.

3.1.11 Able to swallow and retain oral medication, *and must not have any clinically significant gastrointestinal abnormalities that may alter absorption such as malabsorption syndrome or major resection of the stomach or bowels*

3.2 Exclusion Criteria

3.2.1 Patients who received prior systemic anti-cancer therapy (chemotherapy with delayed toxicity, extensive radiotherapy, immunotherapy, biologic therapy, or vaccine therapy) within the last 3 weeks prior to Day 1 of Cycle 1. Patients are permitted to be on dabrafenib and trametinib at start of therapy without wash-out period prior to Day 1 of Cycle 1. Dosing will change to protocol determined dose levels on Day 1 of Cycle 1

3.2.2 Patients must not have received prior JAK1 inhibitor therapy.

3.2.3 Patients who are receiving any other investigational agents. Patients who have taken an investigational drug within 28 days or 5 half-lives (minimum 14 days), whichever is shorter, prior to registration.

3.2.4 Patients with history of RAS mutation-positive tumors are not eligible regardless of interval from the current study. Prospective RAS testing is not required. However, if the results of previous RAS testing are known, they must be used in assessing eligibility.

3.2.5 Patients must have no clinical evidence of leptomeningeal or brain metastasis causing spinal cord compression that are symptomatic, untreated, not stable for \geq 4 weeks prior to Day 1 of Cycle 1 (must be documented by imaging), or requiring corticosteroids to manage metastasis-related symptoms. Subjects who have been off of corticosteroids for at least 2 weeks prior to Day 1 of Cycle 1 or are on a stable dose of \leq 10 mg per day of a prednisone equivalent for >1 month prior to Day 1 of Cycle 1 can be enrolled. Subjects must also be off of enzyme-inducing anticonvulsants for >4 weeks prior to Day 1 of Cycle 1.

3.2.6 History of known immediate or delayed hypersensitivity reactions attributed to compounds of similar chemical or biologic composition to INCB039110, dabrafenib, or trametinib, or excipients or to dimethyl sulfoxide (DMSO).

3.2.7 Uncontrolled intercurrent illness including, but not limited to, ongoing or active serious infection, symptomatic congestive heart failure, unstable angina pectoris, cardiac arrhythmia, uncontrolled diabetes, or psychiatric illness/social situations that would limit compliance with study requirements.

3.2.8 Pregnant women are excluded from this study because INCB039110, dabrafenib, and trametinib may have teratogenic or abortifacient effects. Because there is an unknown but potential risk for adverse events in nursing infants secondary to treatment of the mother with the study drugs, breastfeeding should be discontinued *prior to* the mother being treated with the study drugs.

3.2.9 History of interstitial lung disease or pneumonitis.

3.2.10 Patients known to be HIV-positive patients and on combination antiretroviral therapy are ineligible because of the potential for pharmacokinetic interactions with the study drugs. In addition, these patients are at increased risk of lethal infections when treated with marrow-suppressive therapy. Appropriate studies will be undertaken in patients receiving combination antiretroviral therapy when indicated.

3.2.11 History of another malignancy other than the study indication under this trial within 5 years of study enrollment, with the exception of the following:

- Subjects who underwent successful definitive resection of basal or squamous cell carcinoma of the skin, superficial bladder cancer, *in situ* cervical cancer, *in situ* breast cancer, or other *in situ* cancers.
- Subjects who have had a localized (i.e. no history of regional or metastatic spread) solid tumor malignancy \geq 3 years within study enrollment and, in the opinion of the investigator, has a very low probability of recurrence.

3.2.12 History or current evidence/risk of retinal vein occlusion (RVO) or retinal pigment epithelial detachment (RPED):

- History of RVO or RPED, or predisposing factors to RVO or RPED (e.g., uncontrolled glaucoma or ocular hypertension, uncontrolled systemic disease such as hypertension, diabetes mellitus, or history of hyperviscosity or hypercoagulability syndromes).
- Visible retinal pathology as assessed by ophthalmic exam that is considered a risk factor for RVO or RPED such as evidence of new optic disc cupping, evidence of new visual field defects, and intraocular pressure >21 mm Hg.

3.2.13 History or evidence of cardiovascular risk including any of the following:

- A QT interval corrected for heart rate using the Bazett's formula QTcB ≥ 460 msec on the pre-study baseline single 12 lead EKG.
- History or evidence of current clinically significant uncontrolled arrhythmias (exception: patients with controlled atrial fibrillation for >30 days prior to registration are eligible).
- History of acute coronary syndromes (including myocardial infarction and unstable angina), coronary angioplasty, or stenting within 6 months prior to registration.
- History or evidence of current \geq Class II congestive heart failure as defined by the New York Heart Association (NYHA) functional classification system
- Treatment-refractory hypertension defined as a blood pressure of systolic >140 mmHg and/or diastolic >90 mmHg which cannot be controlled by anti-hypertensive therapy. In patients with no history of hypertension and a pre-study baseline blood pressure of systolic >140 mmHg and/or diastolic >90 mmHg, a second reading must be taken at least 1 minute later, with the two readings averaged to obtain a final BP measurement.
- Abnormal cardiac valve morphology (\geq grade 2) documented by echocardiogram (subjects with grade 1 abnormalities [i.e., mild regurgitation/stenosis] can be entered on study). Subjects with moderate valvular thickening should not be entered on study.
- Prior placement of an implantable defibrillator
- History of or identification on screening imaging of intracardiac metastases

3.2.14 No known active infection with Hepatitis B Virus (HBV), or Hepatitis C Virus (HCV). Patients with chronic or cleared HBV infection and HCV infection are eligible.

3.2.15 For patients requiring anti-coagulation with vitamin K antagonists, therapeutic level dosing of warfarin can be used with close monitoring of PT/INR by the site. Exposure may be decreased due to enzyme induction when on treatment, thus warfarin dosing may need to be adjusted based upon PT/INR. Consequently, when discontinuing dabrafenib, warfarin exposure may be increased and thus close monitoring via PT/INR and warfarin dose adjustments must be made as clinically appropriate. If clinically indicated, prophylactic low dose warfarin may be given to maintain central catheter patency.

3.2.16 Current use of a prohibited medication. The following medications or non-drug therapies are prohibited

- Other anti-cancer therapy while on study treatment. (note: megestrol [Megace] if used as an appetite stimulant is allowed).
- Concurrent treatment with bisphosphonates is permitted; however, treatment must be initiated prior to the first dose of study therapy. Prophylactic use of bisphosphonates in patients without bone disease is not permitted, except for the treatment of osteoporosis.

- Because the composition, PK, and metabolism of many herbal supplements are unknown, the concurrent use of all herbal supplements is prohibited during the study (including, but not limited to, St. John's wort, kava, ephedra [ma huang], ginkgo biloba, dehydroepiandrosterone [DHEA], yohimbe, saw palmetto, or ginseng).
- Patients receiving any medications or substances that are strong inhibitors or inducers of CYP3A or CYP2C8 are ineligible. Current use of, or intended ongoing treatment with: herbal remedies (e.g., St. John's wort), or strong inhibitors or inducers of P-glycoprotein (Pgp) or breast cancer resistance protein 1 (Bcrp1) should also be excluded. Below are a few examples of the agents.

PROHIBITED – strong inducers of CYP3A or CYP2C8, since concentrations of dabrafenib may be decreased	
Class/Therapeutic Area	Drugs/Agents
Antibiotics	Rifamycin class agents (e.g., rifampin, rifabutin, rifapentine),
Anticonvulsant	Carbamazepine, oxcarbazepine phenobarbital, phenytoin, s-mephénytoïn
Miscellaneous	bosentan, St. John's wort
PROHIBITED – Strong inhibitors of CYP3A, or CYP2C8 since concentrations of dabrafenib may be increased	
Class/Therapeutic Area	Drugs/Agents
Antibiotics	Clarithromycin, telithromycin, troleandomycin
Antidepressant	Nefazodone
Antifungals	Itraconazole, ketoconazole, posaconazole, voriconazole, fluconazole
Hyperlipidemia	Gemfibrozil
Antiretroviral	ritonavir, saquinavir, atazanavir
Miscellaneous	Conivaptan

Because the lists of these agents are constantly changing, it is important to regularly consult a frequently-updated list such as <http://medicine.iupui.edu/clinpharm/ddis/main-table/>; medical reference texts such as the Physicians' Desk Reference may also provide this information.

As part of the enrollment/informed consent procedures, the patient will be counseled on the risk of interactions with other agents, and what to do if new medications need to be prescribed or if the patient is considering a new over-the-counter medicine or herbal product.

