5.4 General Concomitant Medication and Supportive Care Guidelines

5.4.1 Trametinib

Because there is a potential for interaction of trametinib with other concomitantly administered drugs through the cytochrome P450 system, the case report form must capture the concurrent use of all other drugs, over-the-counter medications, or alternative therapies. After discussion with the Principal Investigator, agents known to affect or with the potential to affect selected CYP450 isoenzymes may be permitted, if clinically indicated.

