5.4.2 Dabrafenib

Because there is a potential for interaction of dabrafenib with other concomitantly administered drugs through the cytochrome P450 system, the case report form must capture the concurrent use of all other drugs, over-the-counter medications, or alternative therapies. The Principal Investigator should be alerted if the patient is taking any agent known to affect or with the potential to affect selected CYP450 isoenzymes. Appendix B is a patient information sheet that can be used for this specific protocol and presented to the patient.

Dabrafenib mesylate is a substrate for CYP 3A4, 2C8, p-glycoprotein (Pgp), and breast carcinoma resistance protein (Bcrp). Strong inhibitors/inducers of these enzymes and transporters are prohibited for eligibility and during the study.

Mild or moderate inhibitors/inducers of CYP 3A4, 2C8, Pgp, and Bcrp should be used with caution as dabrafenib serum concentrations may be altered. Because the lists of these agents are constantly changing, it is important to regularly consult a frequently-updated list such as <http://medicine.iupui.edu/clinpharm/ddis/table.aspx>; medical reference texts such as the Physicians' Desk Reference may also provide this information.

Dabrafenib may induce CYP 3A4, 2B6, and possibly 2C8/9 and 2C19. Use concomitant medications that are substrates of these isoenzymes with caution as there may be loss of efficacy. Substitute with other medications that are not affected if possible.

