1.2. Prohibited Medications and Non-Drug Therapies

The use of certain medications and illicit drugs within 28 days or 5 half lives, whichever is shorter, prior to registration and for the duration of the study will not be allowed.

The following medications or non-drug therapies are also prohibited while on treatment in this study:

- Other anti-cancer therapies;
- Other investigational drugs;
- Antiretroviral drugs (Note: Subjects with known HIV are ineligible for study participation);
- Herbal remedies (e.g., St. John's wort);
- Dabrafenib is metabolized primarily by Cytochrome P450 (CYP) 2C8 and CYP3A4. Co-administration of dabrafenib with ketoconazole, a CYP3A4 inhibition, or with gemfibrozil, a CYP2C8 inhibitor, resulted in increases in dabrafenib AUC of 71% and 47%, respectively. Drugs that are strong inhibitors or inducers of CYP3A and CYP2C8 (see list in Table 1) may only be used under special circumstances (e.g. as a single use for a procedure) while treatment with study drug is interrupted as they may alter dabrafenib concentrations; consider therapeutic substitutions for these medications. The list may be modified based on emerging data. Refer to the SPM for the most current list.

Table 1 Prohibited Medications

PROHIBITED – strong inducers of CYP3A or CYP2C8, since concentrations of dabrafenib may be decreased	
Class/Therapeutic Area	Drugs/Agents
Antibiotics	Rifamycin class agents (e.g., rifampin, rifabutin, rifapentine),
Anticonvulsant	Carbamazepine, oxcarbazepine, phenobarbital, phenytoin, s-mephentoin
Miscellaneous	bosentan, St. John's wort

PROHIBITED – Strong inhibitors of CYP3A, or CYP2C8 since concentrations of dabrafenib may be increased	
Class/Therapeutic Area	Drugs/Agents
Antibiotics	Clarithromycin, telithromycin, troleandomycin
Antidepressant	Nefazodone
Antifungals	Itraconazole, ketoconazole, posaconazole, voriconazole
Hyperlipidemia	Gemfibrozil
Antiretroviral	ritonavir, saquinavir, atazanavir
Miscellaneous	Conivaptan

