1.3. Medications to be Used with Caution

The following medications should be used with caution as their concentrations may be altered by dabrafenib or they may alter dabrafenib concentrations:

- Drugs that are moderate inhibitors or inducers of CYP3A and CYP2C8 as they may alter concentrations of dabrafenib.
- Dabrafenib has been shown to induce CYP3A4 and CYP2C9 in vivo using midazolam (CYP3A4 substrate) and S-warfarin (CYP2C9 substrate). Dabrafenib is an in vitro inducer of CYP2B6 and other enzymes such as CYP2C8, CYP2C19, UDP-glucuronyl transferases. Transporters may also be affected. Co-administration of dabrafenib and medications which are affected by the induction of these enzymes (including warfarin) and transporters may result in loss of efficacy. If co-administration of these medications is necessary, investigators should monitor subjects for loss of efficacy or consider substitutions of these medications. A partial list of these medications is provided in

Table 2 and in the SPM.

- Therapeutic level dosing of warfarin can be used with close monitoring of PT/INR by the site. Exposure decreased by 37% due to enzyme induction when on treatment, thus warfarin dosing may need to be adjusted based upon PT/INR. Consequently, when discontinuing dabrafenib, warfarin exposure may be increased and thus close monitoring via PT/INR and warfarin dose adjustments must be made as clinically appropriate. Prophylactic low dose warfarin may be given to maintain central catheter patency.

Dabrafenib solubility is pH-dependent with decreased solubility at higher pH. Drugs such as proton pump inhibitors that inhibit gastric acid secretion to elevate gastric pH may decrease the solubility of dabrafenib and reduce its bioavailability. No clinical study has been conducted to evaluate the effect of pH on dabrafenib pharmacokinetics. In an ad-hoc analysis, no differences in C_{max} and AUC were noted between subjects who reported taking pH-elevating products relative to other subjects. Due to the theoretical risk that pH-elevating agents may decrease oral bioavailability and

exposure to dabrafenib, these medicinal products that increase gastric pH should be used with caution when administered with dabrafenib

Table 2 Medications to be used with Caution

USE WITH CAUTION: Moderate inhibitors of CYP3A, or CYP2C8 since concentrations of dabrafenib may be increased	
Class/Therapeutic Area	Moderate CYP3A and CYP2C8 Inhibitors
Antiarrhythmics	Diltiazem, verapamil

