Antibiotic	Erythromycin
Antifungal	Fluconazole
Miscellaneous	Aprepitant
USE WITH CAUTION: Co-administration of these drugs with study treatment may result in loss of efficacy. Monitor subjects for loss of efficacy or substitute with another medication.	
Class/Therapeutic Area	CYP3A4, CYP2B6, CYP2C8, CYP2C9, or CYP2C19 Substrates that May be Affected by Induction
Analgesics	Alfentanil, buprenorphine, celecoxib, codeine, fentanyl, methadone, oxycodone
Antiarrhythmics	Disopyramide, dronedarone, mexiletine, propafenone, quinidine
Antibiotics	Chloramphenicol, doxycycline, erythromycin, moxifloxacin
Anticoagulants/ Antiplatelets	Cilostazole, warfarin
Anticonvulsants	Divalproex, lamotrigine, valproate, zonisamide
Antidepressants and Antipsychotics	Aripiprazole, bupropion, buspirone, desipramine, haloperidol, mirtazapine, pimozide, quetiapine, trazodone, amitriptyline, clomipramine, imipramine
Antidiabetics	Glyburide, saxagliptin, tolbutamide, nateglinide, pioglitazone, repaglinide, rosiglitazone
Antifungals	Caspofungin, fluconazole, terbinafine
Antihistamines	Astemizole, chlorpheniramine, ebastine
Antihypertensives	Amlodipine, diltiazem, felodipine, nifedipine, nilvadipine, nisoldipine, verapamil
Antimigraine Agents	Diergotamine, eletriptan, ergotamine
Corticosteroids	Dexamethasone, methylprednisolone, oral budesonide
Erectile Dysfunction Agents	Sildenafil, tadalafil, vardenafil
HMG-CoA Reductase Inhibitors	Atorvastatin, lovastatin, simvastatin
Hypnotics and Sedatives	Alprazolam, brotizolam, diazepam, estazolam, midazolam, triazolam, zolpidem, zopiclone
Immunosuppressants	Everolimus, sirolimus, tacrolimus
Miscellaneous	Aprepitant, cisapride, darifenacin, disopyramide, leflunomide, methohexitol, oral contraceptives, quinine, ranitidine, solifenacin, sulfasalazine, tramadol, tolvaptan, chloroquine, zopiclone
Selective Aldosterone Blockers	Eplerenone

USE WITH CAUTION: Co-administration of drugs that increase gastric pH should be used with caution when administered with dabrafenib..

pH altering agents	dexlansoprazole, esomeprazole, famotidine, ilaprazole, lansoprazole, omeprazole, pantoprazole, rabeprazole, ranitidine
--------------------	--

Abbreviations: CYP = cytochrome P450; HMG-CoA = 3-hydroxy-3-methylglutaryl-coenzyme A.

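### Fluconazole is a prohibited strong inhibitor in 3.2.16 but a caution-only moderate inhibitor in Appendix E, and 8.1 asks only for caution where 5.4.2 prohibits strong CYP agents (minor)

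*Combined protocol and SAP*

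**What the plan says.** **Fluconazole.** Section 3.2.16 has a table of prohibited strong CYP3A or CYP2C8 inhibitors. Its antifungal row reads "Itraconazole, ketoconazole, posaconazole, voriconazole, fluconazole". Appendix E Table 1, also a list of prohibited strong inhibitors, gives the row as "Itraconazole, ketoconazole, posaconazole, voriconazole". Appendix E Table 2 has a block headed "USE WITH CAUTION: Moderate inhibitors of CYP3A, or CYP2C8 since concentrations of dabrafenib may be increased", and one of its rows is "Antifungal Fluconazole".

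**What the class decides.** Section 5.4.2 ties the rule to inhibitor strength. For strong agents: "Strong inhibitors/inducers of these enzymes and transporters are prohibited for eligibility and during the study". For weaker ones: "Mild or moderate inhibitors/inducers of CYP 3A4, 2C8, Pgp, and Bcrp should be used with caution as dabrafenib serum concentrations may be altered".

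**Strong agents in other sections.** Section 8.1 (dabrafenib, potential drug interactions) asks for caution if strong CYP2C8 or CYP3A4 inducers or inhibitors are given together with dabrafenib. Appendix E 1.2 allows strong agents only in special circumstances and only while study drug is interrupted.

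**The concern.** A patient on study treatment may need an antifungal. A site that reads 3.2.16 together with 5.4.2 concludes that fluconazole is not allowed. A site that opens Appendix E, the appendix devoted to concomitant medication, concludes that it may be given with caution. Two sites could therefore act differently under one protocol, and the text does not settle whether giving the drug alongside dabrafenib is a deviation.

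The 8.1 sentence raises the same problem for the whole strong class. Taken alone, it would let a site give a strong inhibitor or inducer alongside dabrafenib with caution, which 5.4.2 forbids. The protocol's own background shows why the prohibition exists: section 2.3.2 reports dabrafenib AUC increases of 71% with ketoconazole and 47% with gemfibrozil. These are rules about what a patient may take while being dosed, so a contradiction between them deserves correction even when it is small.

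**Working it through.** There is no statistical figure to reproduce. The check is a comparison of the lists, drug by drug, followed by a reading of the rules.

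**Step 1: compare the prohibited lists.**

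| Class | 3.2.16 | Appendix E Table 1 |
|---|---|---|
| Antibiotics | 3 | 3 |
| Antidepressant | 1 | 1 |
| Antifungals | 5 | 4 |
| Hyperlipidemia | 1 | 1 |
| Antiretrovirals | 3 | 3 |
| Miscellaneous | 1 | 1 |
| **Strong inhibitors, total** | **14** | **13** |

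The only drug in the first list and not in the second is fluconazole. No drug is in the second and not in the first. The named strong inducers number 3 + 5 + 2 = 10 in each list, and all match. The two tables are otherwise the same list.

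**Step 2: look for the prohibited drugs in the caution table.** The moderate-inhibitor block of Appendix E Table 2 names five drugs: diltiazem, verapamil, erythromycin, fluconazole and aprepitant. Of the 14 strong inhibitors in 3.2.16, only fluconazole is among them. None of the 13 in Appendix E Table 1 appears in Table 2, so Appendix E agrees with itself. The disagreement is between Appendix E and 3.2.16.

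**Step 3: apply the 5.4.2 rule to each label.**

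| Source of the label | Class of fluconazole | Answer on treatment under 5.4.2 |
|---|---|---|
| 3.2.16 table | strong inhibitor | prohibited |
| Appendix E Table 2, inhibitor block | moderate inhibitor | caution |

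The two answers cannot both hold. At entry there is no practical conflict, because the 3.2.16 exclusion applies directly.

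**Step 4: look for a rule of precedence.** Section 3.2.16 calls its entries a few examples and sends sites to a website and reference texts. Section 5.4.2 also points to a regularly updated outside list. Appendix E 1.2 points to the SPM. None of these says which printed list prevails when they differ, and what the outside sources say about fluconazole cannot be seen from the documents.

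**Step 5: set 8.1 against 5.4.2.** Both concern strong CYP2C8 and CYP3A4 agents and dabrafenib. Section 5.4.2 forbids them at eligibility and during the study; 8.1 contemplates giving them together with dabrafenib, with caution. This is a direct contradiction and does not depend on how any single drug is classed.

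**The case against.** The strongest reply is that 3.2.16 is an entry criterion, while Appendix E 1.2 is expressly about drugs prohibited on treatment and Appendix E is consistent with itself. A site could use one at entry and the other afterwards. The operative rule would then be functional: look up the drug's strength in a current source, and treat the printed names as illustrations. Investigator oversight also helps. Section 5.4.2 asks that the Principal Investigator be alerted to CYP-active agents, and the study calendar schedules review of concurrent medication at visits.

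Much of this stands, and it limits the point. It would be too strong to say that no written rule exists. The rule by strength is clear, and only the printed classification of one drug is in doubt. The reply does not remove the conflict, however. Section 3.2.16 labels fluconazole strong, and 5.4.2 carries the ban on strong agents into the treatment period. A site that finds the drug named has little reason to look further.

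Three stronger readings are tempting, and the documents do not support them.

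- *The second Table 2 entry is a further contradiction.* The row "Caspofungin, fluconazole, terbinafine" lists fluconazole as a substrate whose own efficacy may fall through induction. That is a different interaction and says nothing about inhibitor strength.
- *Section 5.4.1 also loosens the ban.* Its sentence that "agents known to affect or with the potential to affect selected CYP450 isoenzymes may be permitted, if clinically indicated" sits under trametinib, requires discussion with the Principal Investigator and states no rule for strong agents. The specific dabrafenib prohibition is naturally read as controlling.
- *Appendix E 1.2 allows strong agents alongside study drug.* It requires study drug to be interrupted, so it still bars giving them together. It is a narrow exception to 5.4.2.

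**Conclusion.** The plan is wrong as written on two small matters. First, the printed lists give fluconazole two inhibitor classes, and through 5.4.2 these lead to opposite instructions during treatment with no stated precedence. Second, the caution sentence in 8.1 contradicts the prohibition in 5.4.2. The extent is 1 of 14 named strong inhibitors and one sentence. The severity is minor, since 5.4.2 states the general ban plainly and the Principal Investigator would probably hear of a case.

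The conclusion rests on the printed text alone. It does not assume which class is pharmacologically right: either 3.2.16 or Appendix E could hold the stray entry.

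A reader might infer that the mismatch threatens the dose-finding result through raised dabrafenib levels. The documents do not support that. They give AUC increases for ketoconazole and gemfibrozil but none for fluconazole, and they do not indicate how often it would be used. No effect on exposure from fluconazole, on DLT rates or on the MTD is claimed.

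**What to change.** 1. Have the sponsor's clinical pharmacology team assign fluconazole one inhibitor class, and make 3.2.16 and Appendix E Tables 1 and 2 agree.
   - If strong: add it to Table 1 and remove it from the moderate-inhibitor row of Table 2.
   - If moderate: delete it from the 3.2.16 table and leave Appendix E as it is.
   - Until this is settled, treat it as prohibited. This is an interim precaution, not a judgement on the class.
2. In 8.1, replace the caution sentence on strong CYP2C8 and CYP3A4 agents with the 5.4.2 prohibition, and cross-refer to the Appendix E 1.2 exception (special circumstances, study drug interrupted).

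The cost is one or two table entries and one sentence, in a single amendment. It needs no added visits, samples or data fields, and no change to the statistical section.
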